In years 3-5 of the proposed project, we will conduct a Stage 1 randomized clinical trial evaluating the program in which 90 Spanish-speaking individuals with alcohol use disorder will be randomized to (1) standard outpatient counseling at the Hispanic Clinic (ST; typically consisting of weekly individual and group supportive counseling) or (2) CBT4CBT-Spanish as an adjunct to ST. Other aspects of the trial will parallel those in our completed trial of the English version of CBT4CBT-Alcohol¹⁶ to facilitate comparability across studies. Treatments will be delivered over an 8-week period with a 6-month follow-up to assess durability and/or delayed emergence of treatment effects. The primary outcome measure will be percent days of

abstinence (PDA) by week. Secondary outcomes include percent heavy drinking days and number of individuals with no heavy drinking days in the last 4 weeks of treatment¹⁹.

2. Participants

Participants will be 90 individuals seeking treatment for alcohol use at the Hispanic Clinic of CMHC. The clinic treats a heterogeneous population, where 42% of those in the co-occurring treatment program report alcohol as their principal substance related issue and 43% are women. As reported above, we have demonstrated our ability to recruit, randomize, retain, and follow-up high numbers of closely related samples in this setting^{191, 192}.

a. Inclusion and exclusion criteria

Participants will be included who are (1) 18 years of age or older, (2) applying/referred for outpatient alcohol treatment, (3) meet current DSM-IV/DSM-5 criteria for alcohol use disorder with use in the past 30 days, (4) speak Spanish as their preferred or principal (most commonly spoken) language, (5) sufficiently stable for 8 weeks of outpatient treatment, and (6) willing to provide locator information and be contacted for follow-up for 6 months. Individuals will be excluded who (1) have an untreated/unstable bipolar or schizophrenic disorder, or (2) have a current legal case pending such that incarceration during the 8-week protocol is likely. Those physically dependent on alcohol can be rescreened following detoxification/stabilization (see Human Subjects).

b. Rationale for sample choice (also see Human Subjects section).

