Follow-up interviews will be conducted 1, 3, and 6 months after termination of treatment. Follow-up interviews will include the full posttreatment battery (see Assessments, below), including assessment of utilization of other treatments and services received. We will attempt to follow all participants in the intent to treat sample, regardless of their retention in treatment, using strategies that have been successful in multiple previous studies. These include: (a) thorough explanation at the initial consent interview to participants of the importance of follow-ups, (b) requiring that each participant provide at least 3 *verified* locators who are likely to have knowledge of their whereabouts throughout follow-up, (c) use of multiple sources and locators to track participants²⁰⁷, and (d) payment to participants of \$50 for each completed follow-up interview, with additional monetary incentives for completing consecutive interviews on time. Using these procedures, our current rate of follow-up approaches 90-98% across studies^{16, 126}. Thus, we have been successful in conducting true intent-to-treat analyses^{208, 209} in that the samples include post-treatment and follow-up data from all participants randomized, including those who have dropped out of treatment.

4. Treatments

a. Standard treatment as usual (ST)

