c. *Evaluation of treatment effects at posttreatment and follow-up*: The principal strategy for assessing the efficacy of the study treatments on outcome over time will be random effects regression models for continuously measured primary (e.g. percent days of abstinence by week) and secondary (e.g., acquisition of coping skills) outcome variables. The focus of the repeated measures analyses will be the 'contrast by time effects', which essentially evaluates whether the slopes, or rates of change, of one group differ from the slopes of another group. We have used these methods to evaluate main and interaction effects, with appropriate covariates (e.g., retention, compliance with treatment, time spent working with the CBT4CBT program) in multiple previous trials^{14, 151, 160, 200, 201, 254}. Follow-up data will be analyzed using random-effects regression modeling²⁵⁵ for our primary outcome measures across time, using the contrasts described above, with appropriate covariates (e.g., length of time in treatment, exposure to other treatment during follow-up). Random effects regression models have several advantages in follow-up data from clinical trials of substance users where participants are unlikely to attend follow-up evaluations precisely at the desired fixed points, and are less vulnerable than traditional MANOVA approaches to missing data^{208, 209, 251, 252}. As in our previous trials^{16, 126}, we estimate that our extensive efforts to track participants will yield a 90% follow-up rate.

d. *Adequacy of sample size*: This Stage 1 trial is intended to provide initial pilot testing and feasibility testing of the web-based CBT4CBT program in a Spanish-speaking sample of individuals with alcohol use disorder. Based on SSize software, the proposed sample sizes will enable us to detect effect sizes of .35 or higher for either hypothesis, which will be the criterion for determining whether CBT4CBT-Spanish-Alcohol has adequate promise to justify a fully powered randomized trial²⁵⁶. This sample size was sufficient for the English-language trials of the drug and alcohol versions of CBT4CBT, which yielded effect sizes of .46-.59^{13, 15, 16}.

Power calculations for random effects regression	Power	Estimated effect size	Estimated ICC	# of datapoints	Sample size per cell
H1: (CBt4CBT-S + ST) v ST, main effect for active treatment phase (assessed weekly, baseline-8weeks)	.80	.35	.40	9	45

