H2: (CBT4CBT-S + ST) vs ST, main effect for follow-up (assessed monthly, end of treatment-6 months)	.80	.50	.80	7	40

2. Treatment specificity and mediators

We will explore the extent to which participants improve coping skills over time using the ARRT as described above and the extent to which acquisition of coping skills may mediate outcome for CBT4CBT-Spanish-Alcohol in this sample. We have described our use of these models and strategies to evaluate treatment mediators in Preliminary Studies, above, and in several papers^{13, 105, 108, 151}. Following the general analytic framework outlined by Kraemer²⁵⁷, we will use the product of the coefficients method to evaluate the relationship between the mediator (e.g., acquisition of CBT-specific coping skills as measured by the ARRT), or indirect effect, and outcome^{155, 156, 258}. After running a regression equation to determine (1) the effect of treatment on the mediator (provides beta weight for a), we will evaluate (2) the strength of the relationship between the mediator, treatment, and outcome (provides beta b). Using MacKinnon's software PRODCLIN²⁵⁹, we will evaluate the asymmetric confidence intervals for the product of the regression estimates (a^*b).

SECTION VI: RESEARCH INVOLVING DRUGS, BIOLOGICS, PLACEBOS AND DEVICES

If this section (or one of its parts, A or B) is not applicable, state N/A and delete the rest of the section.

N/A

SECTION VII: HUMAN SUBJECTS

1. Subject Population:

Provide a detailed description of the types of human subjects who will be recruited into this study.

Participants will be individuals seeking outpatient treatment for alcohol use at the Connecticut Mental Health Center (CMHC), where the majority of clients are male (73%), middle aged (62%), unemployed (71%), unmarried (56%), and have not completed high school (64%). Spanish-speaking participants will be recruited from two CMHC outpatient programs (The Hispanic Clinic at [name] and the Substance Abuse Treatment Unit at [name]) or Connecticut Mental Health Center clinicians. Additionally, MAAS (The Multi- Cultural Ambulatory Addiction Service at [name]) has been appointed a recruitment site

2. Subject classification:

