### **1. Determination of Treatment Outcomes**

*a. Data reduction:* Primary outcome variables have been defined *a priori* to reduce the risk of Type I error. Preparatory analyses include evaluation of baseline equivalence of treatment groups on demographic and prognostic variables and comparability of rates of data availability across conditions.

*b. Strategies for management of differential attrition:* Data analyses will be conducted on the intent-to-treat sample and we will attempt to follow all participants regardless of their retention in treatment. We have established our ability to contact and follow participants who drop out of treatment and to conduct true intent-to-treat analyses, including supplemental analyses that account for whether data was collected before or after dropout/withdrawal. While we anticipate that assertive efforts to locate and interview participants who drop out of treatment will result in low numbers of missing participants and minimal missing data in the final dataset, we will minimize the impact of missing data through the use of random effects regression modelling.

*c. Evaluation of treatment effects at posttreatment and follow-up:* The principal strategy for assessing the efficacy of the study treatments on outcome over time will be random effects regression models for continuously measured primary (e.g. percent days of abstinence by week) and secondary (e.g., acquisition of coping skills) outcome variables. The focus of the repeated measures analyses will be the 'contrast by time effects', which essentially evaluates whether the slopes, or rates of change, of one group differ from the slopes of another group. We have used these methods to evaluate main and interaction effects, with appropriate covariates (e.g., retention, compliance with treatment, time spent working with the CBT4CBT program) in multiple previous trials. Follow-up data will be analyzed using random-effects regression modeling for our primary outcome measures across time, using the contrasts described above, with appropriate covariates (e.g., length of time in treatment, exposure to other treatment during follow-up). Random effects regression models have several advantages in

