follow-up data from clinical trials of substance users where participants are unlikely to attend follow-up evaluations precisely at the desired fixed points, and are less vulnerable than traditional MANOVA approaches to missing data. As in our previous trials , we estimate that our extensive efforts to track participants will yield a 90% follow-up rate.

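### The follow-up test (H2) does not use drinking recorded during treatment, so a randomised participant with no value from week 8 onward drops out of an analysis called intent-to-treat

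*SAP*

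**What the plan says.** SAP 1.b sets the population: "Data analyses will be conducted on the intent-to-treat sample and we will attempt to follow all participants regardless of their retention in treatment". Its protection against missing data is random effects regression; it names no missingness assumption. SAP 1.c (repeated in Protocol Section V.5, item 1.c) then handles the follow-up period in a sentence of its own: "Follow-up data will be analyzed using random-effects regression modeling", "with appropriate covariates (e.g., length of time in treatment, exposure to other treatment during follow-up". Drinking at baseline or during treatment is not among the example covariates.

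The power table in Protocol V.5, item 1.d, separates the two tests by window. H1 is the "main effect for active treatment phase (assessed weekly, baseline-8weeks", with 9 datapoints and 45 per cell. H2 is the "main effect for follow-up (assessed monthly, end of treatment-6 months", with 7 datapoints and 40 per cell. The sample is "90 Spanish-speaking individuals with alcohol use disorder will be randomized to" two arms, and SAP 1.c adds that "we estimate that our extensive efforts to track participants will yield a 90% follow-up rate".

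Three other provisions matter here. SAP 1.a compares data availability between arms. SAP 1.b mentions supplemental analyses that distinguish data collected before and after a participant leaves treatment. The protocol plans a week-8 interview for everyone (Termination and posttreatment assessment), and the assessment table schedules the Timeline Follow Back weekly, at week 8 and at 1, 3 and 6 months.

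**The concern.** A random-effects model tolerates incomplete records because a person's observed outcomes inform the missing ones. That works only for outcomes inside the same model. If H2 is fitted to the window from end of treatment onward, a person with nothing in that window has no record to borrow from, and up to eight weekly PDA values already collected are left unused. For such people the comparison is the same as one restricted to those with data.

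This does not fit the team's own idea of a true intent-to-treat analysis. In the Follow-up section the protocol describes earlier trials in which "the samples include post-treatment and follow-up data from all participants randomized, including those who have dropped out of treatment".

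The third aim, durability, rests on this test. If heavier drinkers during treatment are harder to reach afterwards, and more so in one arm, the estimate moves although data that could correct it are in hand. SAP 1.a would show unequal data availability, but no analysis follows from that finding. The supplemental analyses in 1.b concern the timing of collected data and do not reach people who have none in the window.

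**Working it through.** **1. The plan's 40 per cell.** Inputs from the H2 row: effect .50, ICC .80, 7 datapoints, power .80. Alpha and sidedness are not stated; .05 is assumed.
- Variance of a person's mean: (1 + 6 × .80)/7 = .829.
- n per arm = 2 × .829 × (z_alpha + z_power)² / .50². One-sided: 2 × .829 × (1.645 + .842)² / .25 = 41, with power .79 at 40. Two-sided: 53, with power .69 at 40.
- Attrition: .90 × 45 = 40.5.

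The 40 therefore fits a one-sided calculation and also the 90% follow-up estimate. It is a power input reduced for expected loss.

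**2. Who leaves the H2 model.** Seven monthly points from end of treatment to 6 months are the end-of-treatment point plus months 1 to 6.
- Week-8 value, no later interview: stays in through one point.
- No week-8 value, reached at 1, 3 or 6 months: stays in.
- Nothing from week 8 onward: leaves, whatever was recorded in weeks 1 to 7.

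**3. Size of the shift.** The documents give neither the correlation between phases nor the loss mechanism, so both are assumed. The simulation used 400,000 per arm.
- True effect .35 SD in both phases.
- Variance of the on-treatment mean, 8 weeks at ICC .40: (1 + 7 × .40)/8 = .475.
- Variance of the follow-up mean, 3 visits at ICC .80: (1 + 2 × .80)/3 = .867.
- Correlation r between the two means: .5 or .7.
- Loss is logistic in the on-treatment mean, 10% overall, log-odds 1 per SD (1.5 where only one arm is affected).

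Among those retained, each arm's follow-up mean moves by r × √.867 × (average standardised on-treatment PDA of those retained). The estimate is .35 plus the difference between the arms' movements, so equal movements cancel.

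Estimates when those lost have no value in the window:

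| Loss, standard treatment / CBT4CBT | r = .5 | r = .7 |
|---|---|---|
| 15% / 5% | .315 | .299 |
| 5% / 15% | .394 | .409 |
| 10% / 10%, related to drinking in one arm only, estimate lowered | .298 | .275 |
| 10% / 10%, related to drinking in one arm only, estimate raised | .411 | .434 |

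Equal loss, equally related to drinking, gave about .35.

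Re-running the same scenarios with the end-of-treatment point in the model:
- week-8 value for half of those lost: about .31 to .39 (shift about .04; .045 in one run);
- week-8 value for all: about .34 to .36 (shift about .01);
- on-treatment PDA in the model: about .35 throughout.

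**4. A harsher set of assumptions.** True follow-up effect .50; in most scenarios loss falls on the lowest on-treatment PDA values outright; correlation of the phases' person effects .3 to .9. The shift was 0 to .15 SD using months 1 to 6 only, at most about .035 SD with the end-of-treatment point observed for all, and about 0 with treatment-phase data.

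**5. Scale.** The protocol takes .35 as its criterion of promise for either hypothesis. Against it, .01, .04 and .08 are 3%, 11% and 23%. The standard error of H2 at 40 per arm is √(2 × .829/40) = .20 SD, so .08 is about 0.4 of a standard error.

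**The case against.** The strongest reply is that the plan loses few people. The window opens at end of treatment, a week-8 interview is planned for everyone, and the team reports follow-up of 90 to 98% in earlier studies. The 90% is not defined as per visit or as ever reached; if per visit, fewer than 10% would have no follow-up value at all. This stands. It is why the shift in the design as planned is nearer .01 than .08 SD.

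A reader might infer that 40 per cell means five people per arm are excluded. The documents do not support that: the figure matches a 90% attrition allowance, and SAP 1.b names the intent-to-treat sample. A reader might also infer that the durability estimate is biased. That does not follow either. The shift needs loss, or its link to drinking, to differ by arm; its direction depends on the mechanism; and nothing in the documents says such a difference is expected.

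That treatment-phase drinking stays outside H2 is itself read from the separate windows and the covariate list. The SAP does not expressly forbid a joint model. If one is intended, it has to be written down.

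The full recovery with on-treatment data is partly built in, because simulated loss depended only on a fully observed on-treatment mean. People later lost may also have missed weekly assessments, and then the gain is smaller.

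Finally, the SAP speaks of slope contrasts, so a mean contrast over follow-up could look like a change of estimand. But the power table already calls H2 a main effect, and one joint model can supply either contrast.

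**Conclusion.** The point holds in a limited form. As described, H2 omits any randomised participant with no PDA value from week 8 onward, and the stated missing-data protection does not reach that person. The consequence is conditional: at 10% overall loss, about .01 SD if all have the week-8 value, up to about .04 if half of those lost have it, up to about .08 if none do, and zero when loss is equal and equally related to drinking in both arms. These figures rest on assumed correlations of .5 to .7 and assumed logistic loss; the harsher set reaches .15 SD with no end-of-treatment data. The change should be made because the data are already collected and the remedy is cheap. The trial does not otherwise depend on it.

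**What to change.** Estimate H2 from one mixed model on all 90 randomised participants, with PDA at baseline, during treatment and during follow-up as outcomes. For example, use six occasions (baseline; weeks 1-4; weeks 5-8; follow-up month 1; months 2-3; months 4-6), arm-by-occasion terms, and H2 as the arm contrast over the follow-up occasions. Treatment-phase PDA should enter as an outcome. As a covariate it would not bring back people without follow-up values, and it would adjust away part of the treatment effect.

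The SAP should also state that:
- the H2 analysis set is all randomised;
- data are assumed missing at random given observed drinking;
- the end-of-treatment point does, or does not, belong to the H2 contrast.

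Optionally, lower the predicted follow-up PDA of those still missing in steps and report where the conclusion changes.

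The cost is SAP wording and one model in place of another, with no new data. The downside is an unstructured covariance with 6 × 7/2 = 21 parameters for 90 people. Grouping the weeks keeps it to that, and a simpler structure should be named as the fallback if the model does not converge. Little power should be expected: even complete follow-up on 45 per arm would give .83 one-sided against .79 at 40, and people with only treatment-phase data add less than that.

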Human Investigation Committee Signature

This protocol is valid through

SECTION V: RESEARCH PLAN**1. Statement of Purpose:** State the scientific aim(s) of the study, or the hypotheses to be tested.

The goal of this project is to address a major challenge in health disparities as defined by NIH and the Institute of Medicine, specifically, the need for accessible, effective, evidence-based treatments for Latino/as.

Specific aims are as follows:

- To adapt our existing CBT4CBT program for use with Spanish-speaking alcohol users in a web-based platform
- To conduct an 8-week randomized trial evaluating the feasibility and efficacy of adding CBT4CBT-Spanish to treatment as usual in a community based treatment program in a population of 90 Spanish-speaking individuals who meet current criteria for alcohol use disorder
- To evaluate the long-term durability and/or delayed emergence of treatment effects through a six month follow-up after termination of the study treatments. Given previous evidence regarding the durability of standard clinician-delivered CBT₄₁ and computer-assisted CBT4CBT₂₅, we hypothesize that CBT4CBTSpanish will be significantly more effective than standard treatment alone through the follow-up.

2. Background: Describe the background information that led to the plan for this project.

Provide references to support the expectation of obtaining useful scientific data.

A Health disparities among Latinos, accessibility of evidence based therapies (EBTs).

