Latinos currently represent 17% of the total U.S. population and the figure is expected to almost double by the year 2060²⁴ (NB: we use the term Latino to refer to individuals of Mexican, Puerto Rican, Cuban, Dominican, Central and South American, and Spanish descent). Although recognized as the country's largest ethnic minority group, there is ample evidence that Latinos experience circumstances that limit their access to culturally and linguistically appropriate evidence-based behavioral health treatments, compromising treatment outcomes^{2, 3, 25-27}. This is highly evident in our limited ability to adequately recognize and treat substance use among Spanish-speaking Latinos and alcohol use disorders in particular^{3, 28-30}. Latinos are more likely to engage in heavier drinking and binge drinking than non-Latino Whites, and when they enter treatment, they represent the ethnic minority group at highest risk for dropout³¹⁻³³. Acculturative stressors and socioeconomic disadvantage, particularly unstable housing and limited financial resources, have been associated with poor engagement and low treatment completion rates^{25, 31, 34-37}.

Despite some attention to patterns of substance use among Latinos, most available data focus on prevalence and treatment outcome among Latinos as one group, with very little information on the differences in rates of disorders and treatment outcomes across subgroups³⁸⁻⁴¹. Limited data about a growing, diverse and understudied population underscores the need for research that will shed light on the factors associated with alcohol treatment outcomes among Latinos^{42, 43}. The presence and severity of risk factors such as racism, discrimination, unemployment, and migration-related stress will vary among Latino subgroups; therefore, patterns of use, vulnerability to develop an alcohol use disorder, and treatment responses can also be expected to differ⁴⁴⁻⁴⁷. Understanding the influence of national origin, acculturation, patterns of

consumption and alcohol-related consequences among Latino subgroups is critical to advancing the field of health disparities research and improving treatment outcomes^{28, 37, 48-51}.

B. Why CBT?

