c. Treatment phase

Treatment conditions are described below. Study treatments will last 8 weeks. During the treatment phase, all participants will complete weekly assessments, usually at the time they come in for treatment. Weekly breath and urine sample collection will be supervised by the research assistant. The research assistant conducting weekly and follow-up assessments will be blind to the participants' treatment assignment, using procedures we have worked out in previous trials¹¹².

- *Clinical deterioration.* We will closely monitor participant treatment response and safety in all conditions through weekly assessment sessions. These will include breath and urine screens with assessment of psychiatric status. Although in our experience this is a very rare event in behavioral trials¹¹⁹, including those of computer-assisted therapy^{14, 100}, participants who show significant deterioration (e.g., increased substance use or psychiatric symptoms that cannot be managed within the protocol) will be regarded as symptomatic failures, withdrawn from the treatment arm of the study, and referred appropriately, but will still be followed and included in the intent to treat analysis.
- *Strategies to minimize attrition.* In order to hold participant dropout to a minimum, we use multiple procedures recommended in our manual on enhancing compliance with substance abuse treatment^{205, 206}. These include rapid assignment to study treatments, thorough explanation of study treatments and requirements and a fully bilingual staff, close monitoring of participants' clinical status, integration of the research with the clinical program, accessibility of study staff for questions and problems, and adequate compensation to participants for the time spent on completing assessment instruments.

d. Termination and posttreatment assessment

At the end of the 8-week treatment period, all participants will be re-interviewed by the 'blind' research assistant, who will complete posttreatment ratings (see Assessments, below). Access to the CBT4CBT-Spanish-Alcohol program will be terminated for participants assigned to that condition. Participants in all conditions will be strongly encouraged to continue in treatment at their primary site (Hispanic Clinic, SATU, MAAS).

e. Follow-up

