c. Rationale for design: There are multiple design options for evaluating computer-assisted therapies^{11, 12, 96, 210}. We chose to evaluate CBT4CBT-Spanish-Alcohol as an add-on to standard treatment for several reasons. First, current evidence suggests web-based therapies have enhanced effectiveness when delivered in conjunction with clinician involvement, including our recent trial of CBT4CBT-Alcohol^{91, 92, 105}. Second, evaluation of CBT4CBT-Spanish as an 'add-on' is appropriate given that this will be the first Stage I evaluation of this novel treatment in a new language format for a new population, although it will not control for attention/ time spent. Third, participants may be exposed to some CBT or other EBTs in individual/group sessions as part of standard treatment. Thus, the proposed randomized 'add on' design maximizes the likelihood such exposure is consistent across conditions. Moreover, use of the skill acquisition measure (ARRT, see below) will allow us to evaluate change in CBT skill levels across time in both conditions¹⁸.

Assessments:

Assessments include measures used to: 1) Describe the sample, 2) Measure primary outcomes during treatment and follow-up, and 3) Evaluate likely mediators (e.g., skills acquisition) and moderators (e.g., gender, level of acculturation) in exploratory analyses. We rely on widely used, well-validated instruments, as well as those which have validated Spanish translations (e.g., AUDIT, SCID, Timeline Follow-Back)^{214, 215}; all have been used successfully in our prior studies with Spanish-speaking samples^{160, 216-219}. Hence, only the less well-known instruments are described below; all assessment instruments and the schedule of their administration are listed on the Table.

Instrument name	Interview or self-report	Rater	Screen	Pre Tx	Weekly	Monthly	Post Tx (8 wks)	Follow-up 1, 3 6 mo
Informed Consent Quiz ¹²²	Self-report	P	x					
*PDC Screening Form	Interview	RA	x					
Inclusion/Exclusion criteria	Interview	RA	x					
*Follow-up contact & tracking sheet	Interview	RA	x				x	x
Marins	Self-report	P		x				
Patient Characteristic Form	Interview	RA	x					
Structured Clinical Interview DSM-4/5 (SCID) ²²²	Interview	RA	x				x	
Urn randomization	Interview	RA		x				
Breathalyzer result	Interview	RA	x	x	x		x	x
Urine results	Interview	RA	x	x	x		x	x
CBT Website True/False Quiz	Self-report	P		x			x	x
CBT4CBT Patient Feedback Form	Self-report	P			x			
Treatment Services Utilization	Interview	RA		x		x	x	x

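### The only covariates named for the follow-up models arise after randomisation, and no baseline-only model is made primary

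*SAP*

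**What the plan says.** SAP 1.c, with the same sentence in Protocol Section V.5, 1.c, has the follow-up outcomes analysed by random effects regression, using the same contrasts as the treatment phase and "with appropriate covariates (e.g., length of time in treatment, exposure to other treatment during follow-up". No baseline covariate is named for these models. In the SAP, baseline variables appear only in 1.a, as a preparatory check that the groups are comparable. The urn factors (Protocol Section V.3, B.3.b) govern allocation but are not listed as model terms. No unadjusted or baseline-only version of the follow-up model is designated as primary.

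The documents describe the follow-up effect in two ways. SAP 1.c states: "The focus of the repeated measures analyses will be the 'contrast by time effects", that is, a difference in slopes. The power table in Protocol Section V.5, 1.d describes H2 as "main effect for follow-up (assessed monthly, end of treatment-6 months", with power .80, effect size .50, ICC .80, 7 data points and 40 per cell.

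The follow-up aim (Protocol Section V.1) hypothesises that the program "will be significantly more effective than standard treatment alone through the follow-up". Other treatment is measured repeatedly. The assessment table schedules "Treatment Services Utilization" at pretreatment, monthly, post-treatment and at the 1-, 3- and 6-month follow-ups. The Follow-up section describes the interviews as "including assessment of utilization of other treatments and services received".

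**The concern.** The aim concerns the effect of being assigned to the program. How long a participant stays in treatment, and what other treatment they then receive, are settled after assignment and may be affected by it. If they are, a model holding them equal answers a different question: what the program does at equal treatment length or equal outside care. It would understate a benefit that works through staying in treatment. It would overstate one if the control arm received more outside treatment and that treatment helped. If an unmeasured factor drives both the covariate and drinking, the adjusted estimate is not a clean direct effect either.

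The documents suggest possible routes. The Background says of Latinos entering treatment that "they represent the ethnic minority group at highest risk for dropout". After week 8, "Participants in all conditions will be strongly encouraged to continue in treatment at their primary site", though whether this counts as other treatment is not stated. Participants who deteriorate are withdrawn from study treatment and referred, which the protocol itself calls very rare. None of these shows that the two arms will differ on the covariates.

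**Working it through.** **1. The plan's own figure.** For a repeated-measures main effect with constant ICC, n per arm = 2(z_α + z_β)² × [1 + (m − 1)ICC] / (m d²). H2 supplies d = .50, ICC = .80 and m = 7. The variance factor is (1 + 6 × .80)/7 = 5.8/7 = .829. Neither alpha nor sidedness is stated, so both were tried at 5%.

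- One-sided: 2 × (1.645 + .842)² × .829/.25 = 40.98, so 41 per arm against the stated 40.
- Two-sided: 2 × (1.960 + .842)² × .829/.25 = 52.03, so 53 per arm.

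The stated 40 is therefore close to the one-sided main-effect calculation, which supports reading H2 as a main effect. The gap under a two-sided test comes from the assumed test and has nothing to do with the covariates. The unadjusted standard error at 40 per arm is √(2 × .829/40) = .20.

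**2. Main effect.** Let arm shift the covariate by a SD, and let the covariate change the outcome by g per SD. The documents give neither, so the values below are assumptions. With total effect .50, the adjusted model returns about .50 − a × g.

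| Assumed a | Assumed g | Adjusted main effect |
|---|---|---|
| 0 | any | .50 |
| .2 | .2 | .50 − .04 = .46 |
| .35 | .4 | .50 − .14 = .36 |
| .50 | .4 | .50 − .20 = .30 |
| −.50 | .4 | .50 + .20 = .70 |

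An unmeasured common cause with effect .4 on both covariate and outcome changes the fourth row to .50 − .50 × (.4 + .4 × .4) = .22. That is neither the total effect (.50) nor the direct effect (.30). Simulated random-intercept models (ICC .80, 7 points) agree with the formula: for .3 × .3 and .5 × .3 they gave .42 and .35, against .41 and .35.

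**3. Slope contrast.**

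- *Time-fixed covariate, main effect only.* The covariate adds the same amount at every visit, so it drops out of change over time. At 80 participants without loss, a true slope difference of .050 per month was estimated at .0497 with and without the covariate. With visits at 0, 1, 3 and 6 months and about 10% covariate-dependent loss (the SAP expects 90% follow-up), adjusted and unadjusted contrasts differed by at most .002 on a true difference in change of .50.
- *Covariate-by-time term.* If the covariate alters the slope by .05 per month per SD, a shift of .3 SD gives .050 − .3 × .05 = .035, and a shift of .5 SD gives .025. Simulation agreed.
- *Time-varying covariate.* If arm lowers exposure by .05 or .10 SD per month and exposure is worth .2 per SD, the adjusted slope rises from .050 to about .060 or .069. With the opposite sign it falls.

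**4. Which case applies.** The SAP's slope wording, with time in treatment as a fixed main effect, falls in the unaffected case. The power table's main effect, or repeatedly recorded service use entered by visit, falls in the affected cases. The text does not say which will be fitted.

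**The case against.** The strongest reply is that the SAP's stated contrast is the slope. Time in treatment, if it means the 8-week phase, is fixed once follow-up begins. For that covariate the plain reading of the SAP gives no bias unless a covariate-by-time term is added, and none is mentioned. No section says that other treatment will enter as time-varying. The main-effect reading rests on a row label in the protocol's power table. The covariates are examples, so baseline ones are not excluded. This is also a Stage 1 trial meant to judge promise.

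Most of this stands, and it limits the point to a possibility. It does not remove it, because both affected readings are open in the documents and the only examples given are post-randomisation variables. The intent-to-treat statement does not help: it fixes who is analysed, not what the model conditions on. The supplemental analyses of data before and after dropout are not a baseline-only primary model.

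A reader might infer that the follow-up result will be biased towards the null, or that power will fall to a particular level. The documents do not support either. They give no path sizes and do not show that arm moves either covariate, and the illustrations run in both directions. An adjusted-power range would only restate chosen inputs, so none is given. A reader might also extend the point to the treatment phase, where retention and time on the program are mentioned. That sentence describes what was done in previous trials, and no error is claimed there.

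**Conclusion.** The point holds in limited form, as a cheap improvement. It is certain that the only named follow-up covariates arise after randomisation and that no baseline-only model is primary. It follows that, if arm affects these covariates, adjustment can bias a follow-up main effect, or a slope contrast with a time-varying or time-interacting covariate, as an estimate of the effect of assignment. A slope contrast with a time-fixed main-effect covariate is essentially safe, and without an arm effect on the covariate there is no bias. Size and direction are unknown. The figures from .22 to .70 around a true .50 follow from assumed paths and are not forecasts for this trial.

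**What to change.** State in SAP 1.c and Protocol Section V.5, 1.c that the primary follow-up efficacy model contains arm, time, arm-by-time and only covariates fixed before randomisation, for example the urn factors (gender, education, alcohol severity, computer familiarity and access, acculturation). Move time in treatment and other treatment received to separately labelled exploratory or mediation analyses. Protocol Section V.5, 2 already plans mediation work.

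The cost is one revised sentence in each document, with no new data and no change to the power table. Some precision may be lost if a dropped covariate is strongly prognostic. In simulation the main-effect standard error was .20 unadjusted against .16 to .21 adjusted, and the slope standard error .12 to .13 against .11 to .12. The change does not settle whether the slope or the main effect tests durability; that mismatch between the SAP text and the power table needs its own sentence.
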